Study Protocol Document

Study Title: Diagnostic and Prognostic Value of Reticulated Platelet Fraction in Patients With Ventilator-Associated Pneumonia: A Prospective Observational Study

Protocol ID: KSH-RP-VAP-2025-01

Version Number: 1.0

Date: June 2025

1. Background and Rationale

Ventilator-associated pneumonia (VAP) is a common nosocomial infection in ICU patients undergoing mechanical ventilation for more than 48 hours. Traditional inflammatory markers like CRP and procalcitonin are commonly used but have limitations in early diagnosis. Reticulated Platelet Fraction (RP%) is an emerging biomarker with potential utility in early infection diagnosis and prognosis. This study aims to evaluate the diagnostic and prognostic value of RP% in VAP.

2. Objectives

Primary Objective:

- - To assess the diagnostic accuracy of RP% in patients with VAP.

Secondary Objectives:

- - To evaluate the association between RP% and 28-day mortality.
- - To explore correlations with SOFA scores and antibiotic de-escalation.

3. Study Design

This is a single-center, prospective observational cohort study to be conducted in a tertiary-level ICU. Data will be collected prospectively from patients diagnosed with VAP.

4. Population

Inclusion Criteria:

- - Age \geq 18 years
- - Mechanically ventilated >48 hours
- - Diagnosed with VAP

Exclusion Criteria:

- - Pneumonia at ICU admission or as primary reason for intubation
- - MV duration <48 hours
- - Pregnancy or lactation

- - Hematologic, oncologic, or autoimmune conditions within the past 4 weeks
- - Immunosuppressive therapy or chemotherapy

5. Data Collection and Laboratory Procedures

RP% will be measured via Sysmex XN-1000 using EDTA blood samples, processed within 4 hours. Routine lab values (CRP, PCT, WBCs, etc.) and clinical data (demographics, MV duration, SOFA scores) will be collected from electronic records. Serum for CRP and PCT will be processed via Roche Cobas 8000 after centrifugation.

6. Sample Size

Based on a predicted correlation coefficient ($r=0.5$) between RP% and PCT, a power analysis ($\alpha=0.05$, power=0.95) using G*Power resulted in a required sample size of 38. Considering a dropout margin, a total of 42 patients will be enrolled.

7. Statistical Analysis

Data will be analyzed using SPSS v26. Normality will be assessed via Kolmogorov-Smirnov test. Comparisons will be made using independent samples t-test or Mann-Whitney U test for continuous variables, and Pearson chi-square for categorical data. Correlations will be examined using Pearson or Spearman correlation based on data distribution. A p-value <0.05 will be considered significant.

8. Ethical Considerations

Ethical approval was obtained from the institutional ethics committee of Konya City Hospital. Informed consent will be obtained from all patients' legal representatives.

9. Study Timeline

Start of enrollment: July 2025

Estimated primary completion: January 2026

Study end date: February 2026

10. Principal Investigator

Name: [name]

Institution: Konya City Hospital

Email: [contact]

[contact]

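### The planned unadjusted RP%–SOFA correlation can be partly driven by the platelet count, which may sit on both sides of it

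*Protocol*

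**What the plan says.** Protocol section 1 introduces the marker: "Reticulated Platelet Fraction (RP%) is an emerging biomarker with potential utility in early infection diagnosis and prognosis". Section 2 makes diagnostic accuracy the primary objective. It lists the association with 28-day mortality as one secondary objective and, separately, "To explore correlations with SOFA scores and antibiotic de-escalation". Section 5 gives the source of the scores: "clinical data (demographics, MV duration, SOFA scores) will be collected from electronic records". Section 7 gives the method, "Correlations will be examined using Pearson or Spearman correlation based on data distribution", and the threshold, "A p-value <0.05 will be considered significant".

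The protocol does not say whether the total score or its components will be correlated. It lists no SOFA items, and it mentions no removal of a platelet item and no adjustment for platelet count. Section 4 excludes "Hematologic, oncologic, or autoimmune conditions within the past 4 weeks", which removes some causes of a low platelet count, but a low count is not itself an exclusion.

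**The concern.** A plain two-variable correlation is hard to interpret when both variables are built partly from the same measurement. RP% has the total platelet count in its denominator. The standard SOFA adds points as the platelet count falls. If RP% tends to be higher when platelets are low, the shared count pushes both variables up together, and the coefficient becomes positive with no contribution from the respiratory, cardiovascular, renal or other items.

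What is at stake is what the result can be said to show. A positive RP%–SOFA correlation invites the conclusion that RP% tracks organ dysfunction generally. The stated method cannot separate that from a link with the platelet count alone.

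**Working it through.** **The plan's own figure.** The protocol gives no effect size or power for SOFA. Its only calculation, in section 6, assumes r = 0.5 "between RP% and PCT" with α = 0.05 and "power=0.95) using G*Power resulted in a required sample size of 38". The plain Fisher-z formula, one-sided, gives ((1.645 + 1.645)/0.5493)² + 3 = 38.87, so 39. With the bias correction it gives 38 (power 0.950). Two-sided, the corrected version gives 46. So 38 reproduces as a one-sided test. That is a separate matter; only the enrolment of 42 is used below.

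**Direction of the overlap.** Let R be the reticulated and P the total platelet count, so log RP% = log R - log P + constant. If log R has slope b on log P, then Cov(log RP%, log P) = (b - 1) × Var(log P). This is negative for b < 1, zero for b = 1 and positive for b > 1. The denominator alone does not fix the sign, so an inverse relation has to be assumed.

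**Inputs, none from the documents.**
- Platelets: lognormal, median 150, 200 or 250 × 10⁹/L, log-SD 0.5 or 0.7.
- Platelet item I: 0 to 4, one point for each of the cut-offs 150, 100, 50 and 20 that the count falls below.
- Correlation of RP% with log platelet count: -0.3, -0.5 or -0.7, with 0 as a control.
- Other SOFA points O: mean 7, SD 2, 3 or 4, rounded and kept within 0 to 20, independent of RP% and of platelets.

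**Expected correlation.** With T = O + I and O independent of RP%:

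corr(RP%, T) = corr(RP%, I) × SD(I) / √(SD(I)² + SD(O)²)

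This is exact for Pearson and approximate for ranks. The last column is the Spearman value simulated in 400,000 patients.

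| Case | Median, log-SD | RP%–platelet corr. | SD(O) | Formula | Simulated |
|---|---|---|---|---|---|
| Low | 250, 0.5 | -0.3 | 4 | 0.19 × 0.47 / √(0.47² + 4²) = 0.022 | 0.022 |
| Mid | 200, 0.5 | -0.5 | 3 | 0.38 × 0.64 / √(0.64² + 3²) = 0.079 | 0.078 |
| Extreme | 150, 0.7 | -0.7 | 2 | 0.62 × 0.97 / √(0.97² + 2²) = 0.271 | 0.266 |

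With the platelet item removed, the simulated correlation is 0.00 throughout.

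**Significant results at n = 42** (two-sided 5% Spearman test, 4,000 simulated studies per row; Monte Carlo standard error near 5% is √(0.05 × 0.95/4000) = 0.34 percentage points):

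| Median, log-SD | RP%–platelet corr. | SD(O) | Total SOFA | Platelet item removed |
|---|---|---|---|---|
| 200, 0.5 | 0 | 3 | 5.0% | 4.9% |
| 200, 0.5 | -0.3 | 3 | 6.2% | 5.0% |
| 200, 0.5 | -0.5 | 3 | 8.4% | 5.5% |
| 150, 0.7 | -0.5 | 3 | 13.0% | 5.5% |
| 150, 0.7 | -0.7 | 3 | 21.7% | 5.6% |
| 150, 0.7 | -0.7 | 2 | 39.4% | 4.4% |

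The smallest significant coefficient at n = 42 is 2.021/√(2.021² + 40) = 0.304. Even the extreme expected value of 0.27 lies below it. On average the overlap alone does not reach significance, but it adds to any genuine association and can tip a borderline result.

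**The case against.** The case against is substantial. The protocol never says total SOFA, and a component-wise or adjusted analysis could stand in an analysis plan that is not shown. Both premises come from outside the document: the platelet item from the usual form of the score, and the inverse relation from an assumed correlation. If the reticulated share is constant, or falls with the count, RP% does not rise as platelets fall. The objective is secondary and worded as exploratory, and prognosis has its own objective in 28-day mortality. Section 5 mentions SOFA scores but not item values.

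Most of this stands. It limits the point to a conditional one and keeps it minor. It does not remove it, because section 7 does state a method, and that method has no step that could separate the shared count from the other items.

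A reader might go further and infer that RP% could say nothing about organ failure and still correlate with SOFA, so that the rates above are false-positive rates. That is not supported. On the same assumption, the platelet item is SOFA's coagulation component, so a link through it is a link with one scored organ system, and the correlation with total SOFA is truly non-zero. What may be missing is a link with the other systems.

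**Conclusion.** The point holds in a limited, conditional form. If SOFA is scored in its standard form, if the total is used, and if RP% is inversely related to platelet count at -0.3 to -0.7, the overlap alone produces a correlation of about 0.02 to 0.27. The mid case is about 0.08, with about 8% significant tests at n = 42 against the nominal 5%. About 39% arises only in the corner case of low median platelets, the strongest assumed relation and little spread in the other items. With no relation between RP% and platelet count there is no artefact.

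A reader might also infer that any observed RP%–SOFA correlation would be wholly an artefact, or that the protocol contradicts itself here. The figures do not support the first, since even the largest expected value is below the significance threshold. The document does not support the second, since nothing in it is inconsistent on this point. This is a minor matter of interpretation in an exploratory analysis.

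**What to change.** In Protocol section 7, keep the correlation of RP% with total SOFA and add that it will be reported beside the correlation of RP% with SOFA minus its platelet item. If item scores are not in the records, use a partial correlation with total SOFA given the platelet count. State that a link with organ dysfunction beyond the platelet count will be claimed only if that second version supports it. The platelet-free version removed the overlap in the check above; the partial correlation was not simulated.

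The cost is one extra exploratory analysis, a reduced score that readers know less well, and the need for item-level scores or same-day platelet counts. Section 5 names neither explicitly, so the site should confirm that one of them is available.

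### The primary objective is diagnostic accuracy, but every enrolled patient already has the VAP diagnosis, so specificity, likelihood ratios and a VAP-versus-non-VAP ROC area cannot be estimated

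*Protocol*

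**What the plan says.** - **Protocol, Section 2 (primary objective):** "To assess the diagnostic accuracy of RP% in patients with VAP".
- **Section 2 (secondary objectives):** "To evaluate the association between RP% and 28-day mortality" and "To explore correlations with SOFA scores and antibiotic de-escalation".
- **Section 3:** "Data will be collected prospectively from patients diagnosed with VAP".
- **Section 4 (inclusion criteria):** patients must be "diagnosed with VAP". The criteria for that diagnosis are not given.
- **Title and Section 1:** the title announces "Diagnostic and Prognostic Value of Reticulated Platelet Fraction in Patients With Ventilator-Associated Pneumonia", and Section 1 repeats the claim: "This study aims to evaluate the diagnostic and prognostic value of RP% in VAP".
- **Section 6:** the sample size comes from an anticipated correlation of 0.5 between RP% and PCT (alpha 0.05, power 0.95). This "resulted in a required sample size of 38", raised to 42 for dropout.

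No section names a control, non-VAP or suspected-VAP group, or any reference standard beyond the entry diagnosis.

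**The concern.** Diagnostic accuracy describes how well a test separates people with the condition from people without it. This cohort contains only people with it. The missing comparison is fixed by eligibility, so neither more patients of the same kind nor a later analysis plan can restore it. If the study runs as written, its primary objective goes unanswered and the diagnostic claim in the title and Section 1 has no data behind it.

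The sample size does not help. It rests on the RP%–PCT correlation within VAP, which is not among the listed objectives. That correlation shows whether two markers move together among cases, not whether either one identifies cases.

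**Working it through.** **1. The plan's own figure.** Inputs from Section 6: r = 0.5, alpha 0.05, power 0.95; sidedness is not stated.

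- Fisher z, one-sided: n = ((1.645 + 1.645)/atanh(0.5))² + 3 = 38.9, rounded up to 39.
- Exact bivariate-normal test, one-sided: n = 38, power 0.951. This reproduces the stated 38.
- Exact test, two-sided: n = 46 (power 0.953). Two-sided power is 0.909 at 38 and 0.935 at 42.

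So 38 is a valid one-sided figure for the correlation. It says nothing about diagnostic accuracy.

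**2. What the enrolled patients allow.** Section 4 gives 42 VAP-positive and 0 VAP-negative patients, so TN = FP = 0.

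| Quantity | Formula | Result |
|---|---|---|
| Sensitivity | TP/(TP + FN) | estimable |
| Specificity | TN/(TN + FP) | 0/0, undefined |
| LR+ | sensitivity/(1 − specificity) | undefined |
| LR− | (1 − sensitivity)/specificity | undefined |
| ROC area | based on case/non-case pairs | 42 × 0 = 0 pairs |
| PPV | TP/(TP + FP) = TP/TP | 1 whatever RP% is |
| NPV | TN/(TN + FN) = 0/FN | 0 whatever RP% is |

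**3. How little sensitivity alone tells us.** Choose the RP% value that flags 38 of the 42 cases. Observed sensitivity is 38/42 = 0.905 by construction. Because the cut-off is taken from the same cases, the true sensitivity follows a Beta(38, 5) distribution: mean 38/43 = 0.88, 95% interval 0.77 to 0.96. (For a cut-off fixed in advance, the exact binomial interval for 38/42 is 0.77 to 0.97.)

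Now assume, for illustration, that RP% is normal with equal SD in both groups and that non-VAP patients lie d SD below cases. At the 90%-sensitivity cut-off, specificity = Φ(d − 1.2816) and ROC area = Φ(d/√2).

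| d (SD) | Specificity | ROC area |
|---|---|---|
| 0 | 0.10 | 0.50 |
| 1 | 0.39 | 0.76 |
| 2 | 0.76 | 0.92 |

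The case distribution is the same in all three rows, so the planned data cannot tell them apart.

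**4. Precision if non-cases were added.** Hanley–McNeil standard errors with 42 VAP and 42 non-VAP patients (an assumed number):

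- area 0.65: SE 0.0599, half-width 1.96 × 0.0599 = 0.12
- area 0.75: SE 0.0533, half-width 1.96 × 0.0533 = 0.10
- area 0.85: SE 0.0427, half-width 1.96 × 0.0427 = 0.08

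With 38 evaluable per group the half-widths are 0.12, 0.11 and 0.09.

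**The case against.** The strongest reply is that Section 4 does not define the diagnosis. If it meant a clinical working diagnosis to be confirmed later, some enrolled patients would turn out not to have VAP, and accuracy could be estimated within the cohort. The conclusion does depend on taking the entry diagnosis as the reference. But the protocol mentions no later confirmation and no confirmatory standard. If that was the intention, Sections 3 and 4 would still have to say so.

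A second reply is that Section 7 lists two-group tests and that details belong in the analysis plan. It is fair that unnamed groups in Section 7 are no fault in themselves, and the point does not rest on them. Those tests can serve the secondary objectives, for example survivors against non-survivors. They cannot create a non-VAP group. An ROC curve for 28-day mortality would be possible, but it is prognostic and mortality is already a secondary objective.

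A third reply concerns the remedy. Section 6 does not oblige the sponsor to make the RP%–PCT correlation primary; 28-day mortality is also a within-VAP question. That is true. The correlation is suggested only because it is the quantity the study is sized on. In addition, Section 8 reports ethics approval as obtained and Section 9 plans enrolment from July 2025, so changing the primary objective is a formal amendment and more than an edit.

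**Conclusion.** The concern holds. With the entry diagnosis as reference, which is the only one the protocol offers, the primary objective cannot be met at any sample size. Of the usual accuracy measures only sensitivity is informative, and on its own it is compatible with anything from a useless marker (ROC area 0.50) to a strong one (0.92 at an assumed 2 SD shift). A cut-off giving a fixed sensitivity can be read from the cases, but not one that balances sensitivity against specificity.

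The structural result needs no distributional assumption. The specificity and ROC figures assume normal RP% with equal SD and are illustrative. This must be corrected, because following the plan exactly would leave the diagnostic claim unsupported.

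**What to change.** **Recommended.** Remove diagnostic accuracy from the primary objective and the diagnostic claim from the title and Section 1. Restate the primary objective as a question that VAP patients alone can answer. The one the study is sized on would read: *to estimate the correlation between RP% and PCT in patients with VAP*. It should not be described as diagnostic value. The 28-day mortality objective can stay secondary as stated. Section 6 should then give the test and its sidedness, with the power that follows for r = 0.5 and alpha 0.05:

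| Evaluable n | Pearson, one-sided | Pearson, two-sided | Spearman, one-sided | Spearman, two-sided |
|---|---|---|---|---|
| 38 | 0.95 | 0.91 | 0.92 | 0.87 |
| 42 | 0.97 | 0.93 | 0.95 | 0.90 |

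The Spearman figures are simulated under bivariate normality. They are only a guide for the non-normal data for which Section 7 would choose that test.

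**Cost.** An amendment to the title and Sections 1, 2 and 6, and the loss of the diagnostic claim. No extra patients are needed if one of the powers above is accepted. Two-sided power of 0.95 would need about 46 evaluable patients (Pearson) or 51 (Spearman, same assumption). At the protocol's own margin that is 46 × 42/38 = 50.8, so 51 enrolled, or 51 × 42/38 = 56.4, so 57 enrolled.

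**If the sponsor prefers to keep the diagnostic question,** the protocol needs a non-VAP or suspected-VAP group, a stated reference standard applied blind to RP%, and a new sample-size basis. As an illustration, adding 42 non-VAP patients doubles the study to 84 and gives a 95% interval of about ±0.10 around an assumed ROC area of 0.75 (±0.12 at 0.65, ±0.08 at 0.85).

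### Section 6 sizes the study on an RP%-PCT correlation that is not an objective, so N=38 and power 0.95 do not apply to the primary diagnostic-accuracy objective; the 0.95 also depends on an unstated one-sided test.

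*Protocol*

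**What the plan says.** Section 2 gives one primary objective: "To assess the diagnostic accuracy of RP% in patients with VAP". The secondary objectives are the association of RP% with 28-day mortality and "To explore correlations with SOFA scores and antibiotic de-escalation". PCT appears in none of them; Section 5 lists it among the routine laboratory values.

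Section 6 starts "Based on a predicted correlation coefficient" of 0.5 between RP% and PCT. With alpha 0.05 and power 0.95, G*Power "resulted in a required sample size of 38". It then adds: "Considering a dropout margin, a total of 42 patients will be enrolled". No other power or precision figure appears in the protocol.

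On testing, Section 7 says "Correlations will be examined using Pearson or Spearman correlation based on data distribution" and "A p-value <0.05 will be considered significant". Neither Section 6 nor Section 7 says whether tests are one-sided or two-sided.

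**The concern.** A sample-size section is normally read as the justification for the primary objective. Here a reader would take 38 patients and 0.95 as assurance that the study can answer its diagnostic-accuracy question. A correlation between two blood markers is not a sensitivity, a specificity or an area under the ROC curve, and power to detect the one says nothing about how well the other is estimated. The correlation that was sized is not a secondary objective either.

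The power figure has a smaller problem of its own. Even for the RP%-PCT correlation, 0.95 at 38 holds only under a choice of sidedness that the protocol does not declare.

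**Working it through.** **1. Target of the calculation against the objectives**

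| Question | Section 2 | Section 6 |
|---|---|---|
| Diagnostic accuracy of RP% | Primary | Not sized |
| RP% and 28-day mortality | Secondary | Not sized |
| RP% with SOFA scores and antibiotic de-escalation | Secondary | Not sized |
| RP% with PCT | Not listed | Sole basis for 38 and 0.95 |

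No sample size for accuracy can be derived from the document: it gives no target AUC, sensitivity, specificity or interval width.

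**2. Reproducing 38**

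Inputs from Section 6: r=0.5, alpha=0.05, power=0.95. Assumption: the null value is r=0.

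Exact method (bivariate normal): the critical correlation is r_c = t / sqrt(n − 2 + t²), where t is the upper alpha quantile (one-sided) or alpha/2 quantile (two-sided) of Student's t on n − 2 degrees of freedom. Power is the probability that the sample correlation exceeds r_c when the true value is 0.5; the two-sided test adds the lower tail.

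- One-sided: power is 0.946 at 37 and 0.951 at 38. The smallest N is 38, the protocol's figure.
- Two-sided: power is 0.909 at 38, 0.935 at 42, 0.949 at 45 and 0.954 at 46. The smallest N is 46.

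**3. Check by hand with Fisher's z**

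N = ((z_alpha + z_beta) / atanh(r))² + 3, with atanh(0.5) = 0.5493 and z_beta = 1.645.

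- One-sided: ((1.645 + 1.645) / 0.5493)² + 3 = 38.9, so 39, one above the exact 38.
- Two-sided: ((1.960 + 1.645) / 0.5493)² + 3 = 46.1, so 47, one above the exact 46.
- Two-sided power at 38: Φ(0.5493 × √35 − 1.960) = Φ(1.290) = 0.901.
- Two-sided power at 42: Φ(0.5493 × √39 − 1.960) = Φ(1.470) = 0.929.

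Adding the small-sample bias term r / (2(N − 1)) to atanh(r) gives 38 one-sided and 46 two-sided, in line with the exact results.

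**4. Could another model give 38 two-sided?**

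The noncentral-t (point-biserial) model, which is meant for a dichotomous variable and does not fit two continuous markers, needs 34 one-sided and 42 two-sided (two-sided power 0.934 at 38). It does not return 38 either way.

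**5. The enrolled number**

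The margin is 42 − 38 = 4 patients, or 4/42 = 9.5% of those enrolled. The 42 is the count before losses, so two-sided 0.935 applies only with no dropout. It still falls short of 0.95, because 46 exceeds 42.

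**The case against.** The best reply on sidedness is that Section 6 predicts a positive correlation, so a directional test is a legitimate choice, and that its declaration may sit in a statistical analysis plan that is not at hand. Nothing in Section 7 contradicts one-sided sizing. The two-sided loss is also modest: about 4 percentage points at 38 (0.95 − 0.909) and under 2 at 42 (0.95 − 0.935), on a test that is not a listed objective. This stands, and it makes the sidedness point a clarification. What remains is that Section 6 reports a power that depends on an undeclared choice, while Section 7 gives a bare 0.05 threshold and announces no one-sided testing.

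A second reply is that a small observational study may be sized on a convenient correlation. It may, but the protocol should then say so and not leave the figure standing beside a different primary objective. This part does not depend on an unseen plan, because Sections 2 and 6 both state their position.

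A third reply is that rewording leaves the primary objective unsized. That is true. Data come only from patients "diagnosed with VAP" (Section 3; Section 4 makes the diagnosis an inclusion criterion), and no RP% cut-off is fixed. Those are separate design issues that this change does not repair.

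**Conclusion.** The point holds. The only stated size and power, 38 and 0.95, relate to an RP%-PCT correlation of 0.5 that is not an objective, and they do not apply to the primary objective. Secondarily, 0.95 at 38 is a one-sided result (0.951). If tests are two-sided, power is about 0.91 at 38 and 0.93 at 42, and 0.95 needs 46. These figures assume bivariate-normal data, a null of zero and a true r of 0.5.

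The documents do not support four stronger readings that a reader might infer:

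- *That 38 is an arithmetic error.* It is the exact one-sided answer.
- *That the study is shown to be too small for diagnostic accuracy.* With no accuracy target stated, no required number can be computed. What is shown is that the size has no justification for that objective, not that it is inadequate by a known amount.
- *That an interval for sensitivity at 38 patients would fill the gap.* It would rest on an assumed sensitivity and an unnamed cut-off, and it would suggest that a cohort made up only of VAP patients can answer the accuracy question. No meaningful precision can be stated on that basis.
- *That the Spearman option lowers power by a known amount.* Section 7 chooses the coefficient by data distribution, so figures worked out on normal data would not describe the case in which Spearman is used.

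**What to change.** Wording only, in two sections.

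- **Section 6, target:** state that 38 and 0.95 relate to the RP%-PCT correlation alone, and that the study is neither sized nor powered for diagnostic accuracy.
- **Section 6, sidedness:** state which was used. If tests are two-sided, restate power as about 0.91 at 38 evaluable patients (0.93 at 42 with no dropout).
- **Section 2:** list the RP%-PCT correlation as a secondary objective, labelled as the sizing basis and not as a replacement for the primary objective.

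No extra patients or measurements are needed, since Section 5 already collects PCT. The cost is candour: if tests are two-sided the stated power looks less favourable, and the protocol must admit that its primary objective has no formal size justification.

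### The sample size of 38 gives the stated 95% power only for a one-sided correlation test, which the protocol nowhere declares; read two-sided, power is about 91%

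*Protocol*

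**What the plan says.** Section 6 (Sample Size) rests on a predicted correlation of 0.5 between RP% and PCT, alpha 0.05 and power 0.95. It states the result as "using G*Power resulted in a required sample size of 38". It names neither the G*Power procedure nor the number of tails. It then adds "Considering a dropout margin, a total of 42 patients will be enrolled", without a dropout rate.

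Section 7 (Statistical Analysis) plans Pearson or Spearman correlation, depending on the distribution of the data, and sets one rule for all tests: "A p-value <0.05 will be considered significant". No direction is attached to that rule.

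Section 2 (Objectives) gives the primary objective as "To assess the diagnostic accuracy of RP% in patients with VAP". The only correlation objective is secondary and non-directional: "To explore correlations with SOFA scores and antibiotic de-escalation". Neither one-sided nor two-sided appears anywhere in the protocol.

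**The concern.** A sample-size statement should be reproducible from the inputs printed beside it. Here one input, the sidedness of the test, is missing, and it moves the required number from 38 to 46. A reader who applies the usual two-sided meaning of p < 0.05 will conclude that 38 evaluable patients give 95% power. They do not.

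Two things are at stake. The first is the accuracy of the only power claim in the protocol. The second is the significance threshold for the correlation. If sidedness is left open until the data are seen, a borderline result could be called significant or not according to a choice made afterwards.

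**Working it through.** **Inputs.** From Section 6: r = 0.5, alpha = 0.05, power = 0.95, required N = 38, enrolled N = 42. Assumed, because the protocol does not say: the null correlation is 0, and the two markers are bivariate normal.

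**Method.** The null hypothesis is rejected when the sample correlation exceeds the critical value

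r_crit = t / √(n − 2 + t²),

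where t is the 0.95 quantile (one-sided) or the 0.975 quantile (two-sided) of Student's t with n − 2 degrees of freedom. Power is the integral of the exact density of the sample correlation, with true correlation 0.5, over the rejection region.

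**Critical values at n = 38 (36 df).**
- One-sided: t = 1.688, so r_crit = 1.688 / √(36 + 2.850) = 0.271.
- Two-sided: t = 2.028, so r_crit = 2.028 / √(36 + 4.113) = 0.320.

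**Power at r = 0.5.**

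| n | One-sided | Two-sided |
|---|---|---|
| 37 | 0.9459 | 0.9011 |
| 38 | 0.9507 | 0.9089 |
| 42 | 0.9662 | 0.9347 |
| 45 | 0.9747 | 0.9493 |
| 46 | 0.9770 | 0.9535 |

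**The plan's own figure.** One-sided, power first reaches 0.95 at n = 38, so the stated 38 is reproduced to the integer. Two-sided, the smallest N for 0.95 is 46. A two-sided 90% target would need 37, so as a two-sided number 38 fits a 90% claim rather than a 95% claim.

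**Size of the gap.** At n = 38 the shortfall is 0.95 − 0.9089 = 0.041. The same figure appears as the share of studies with true r = 0.5 whose observed correlation falls between the two critical values: 0.9507 − 0.9089 = 0.042. If all 42 patients are evaluable the shortfall is 0.95 − 0.9347 = 0.015. The correlation detectable with 95% two-sided power is 0.538 at n = 38 and 0.516 at n = 42.

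**Other routes to 38.**
- Fisher z, n = [(z_alpha + z_power) / atanh(0.5)]² + 3 with atanh(0.5) = 0.5493. One-sided: [(1.645 + 1.645) / 0.5493]² + 3 = 38.87, or 39. Two-sided: [(1.960 + 1.645) / 0.5493]² + 3 = 46.07, or 47.
- Point-biserial (noncentral t) model, which does not suit two continuous markers: 34 one-sided and 42 two-sided (power 0.94995 at 41).
- Simulation of the Pearson test at n = 38 (400,000 samples): 0.951 one-sided and 0.910 two-sided.

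The only calculation close to the exact one-sided result is one-sided Fisher z at 39. No two-sided version gives 38 at 95% power.

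**Spearman branch.** Section 7 allows Spearman if the data are not normal. As an illustration under the same bivariate-normal model, simulated two-sided Spearman power is about 87% at 38, 90% at 42 and 93% at 46.

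**The case against.** The strongest reply is that nothing has been miscalculated. The printed inputs and N = 38 agree exactly under a standard test, and no passage declares a two-sided test that this would contradict. The predicted correlation is positive, so a directional test is conceivable, and sidedness is a routine item for a statistical analysis plan, which is not at hand. The shortfall is about 4 points, power remains respectable, and the RP%–PCT correlation is not an objective of the study. On this view the matter is one of wording.

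Much of this is right. The sidedness is undeclared rather than contradicted, the arithmetic is correct for a one-sided test, and the practical effect is modest. The point about deferral does not hold, however. The protocol itself prints a sample size and a power, and the pair is true only under a condition it does not state. A later analysis plan with two-sided tests would leave Section 6 wrong as written.

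A second objection is that a statement that power stays above 90% covers Pearson only. That is also right: under the Spearman branch, two-sided power at 38 falls to about 87%. This narrows the reassurance and makes the shortfall larger.

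**Conclusion.** The concern holds. The figure of 38 is the one-sided answer. Under the ordinary two-sided reading of Section 7, 38 evaluable patients give 90.9% Pearson power for r = 0.5. The stated 95% is not reached even with all 42 (93.5%), because it requires 46. This assumes a null correlation of zero and bivariate normality.

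The statement should be corrected, but the importance is limited. The error concerns how power is described, and it does not undermine the conduct of the study. Correcting it also leaves the primary objective, diagnostic accuracy, without a sample-size basis, since Section 6 powers a different quantity.

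**What to change.** Keep enrolment at 42 and replace the power claim in Section 6 with a sentence such as:

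> With 38 evaluable patients, a two-sided Pearson test at alpha = 0.05 has about 91% power to detect r = 0.5 (95% power for r = 0.54).

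In Section 7, insert the word two-sided into the p < 0.05 rule, so that the power statement and the significance rule share the same sidedness. The new sentence is confined to Pearson; the sponsor may wish to note that power is somewhat lower if Spearman is used.

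If a one-sided test was in fact intended, 38 and 95% can stand, but the protocol must then say so in both sections and justify the direction.

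The cost is one sentence in Section 6 and one word in Section 7. Enrolment, data collection and analysis are unchanged; the stated power becomes less favourable.
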